3.0 STUDY ENROLLMENT AND PARTICIPANT ELIGIBILITY

3.1 Study Enrollment

Patients will be identified as potential candidate and recruited from the GYN-oncology or neuro-oncology clinics in the Cancer Center at Stanford. Once a patient has been identified as a potential candidate and has expressed interest in the study, the neuro-oncology study coordinator will be called. If possible, the neuro-oncology coordinator will obtain consent in a private room in the Stanford Cancer Center or the Women's Cancer Center. Patients may also be consented via telephone or in a private room in the CTRU. Otherwise, a protocol-trained GYN-oncology coordinator or MD will obtain consent. There is no plan for advertising the study outside of Stanford, but patients in GYN-oncology and neuro-oncology will be presented with the study option if appropriate. We do not plan to use any recruitment material.

Informed Consent Process

All participants will be provided a consent form describing the study with sufficient information for participants to make an informed decision regarding their participation. Informed consent will be obtained by trained protocol staff in a private room or via telephone prior to any study procedures. All patients will have sufficient time to ask questions and have them answered prior to signing the form and enrolling in the study. Participants must sign the IRB approved informed consent prior to participation in any study specific procedure. The participant will receive a copy of the signed and dated consent document. The original signed copy of the consent document will be retained in the medical record or research file.

Screen Failures

Screening procedures include the inclusion/exclusion criteria below and a pain scale on the date of DLss testing. These do not include any new laboratory testing which may lead to screen failure. Therefore, the vast majority of patients that are formally screened are likely to enter the

study. Patients who have persistent, elevated pain of ≥ 50 on the day of scheduled testing will be asked to either reschedule or be considered a screen failure if rescheduling is not desired or possible. Patients who need to reschedule testing due to pain on study visit #1 will be considered to have a valid consent if more than 14 days from visit #1. If patient cannot undergo the DLss testing due to pain within the protocol defined window, they will be considered a screen failure. These patients will also be directed to their physician, if needed, for assistance in pain management. In the event that a patient enters screening but subsequently fails to meet criteria, their data will be entered in OnCore as a screen failure.

3.2 Inclusion Criteria

- 3.1.1 Have pathologically proven ovarian cancer or cancer of mullerian origin that requires first-line treatment with a taxane + platinum based chemotherapy regimen.
- 3.1.2 GROUP A (painful neuropathy group): Must have subjective symptoms of painful peripheral neuropathy (burning, stabbing, throbbing, painful tingling, aching in the fingers and/or toes) that is greater than or equal to 10 on a scale of 0 to 100 in the neuropathic pain questionnaire
GROUP B (no pain group): Must either have subjective symptoms of painless neuropathy (loss of sensation, worsening balance, strange sensation in fingers and/or toes) or no complaints related to neuropathy.
- 3.1.3 Be ≥ 18 years of age
- 3.1.4 Have a life expectancy of 6 months
- 3.1.5 Ability to understand the study protocol, participate in testing, and the willingness to sign a written informed consent document.

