Based on these preliminary data, *we propose that the A δ :C pain threshold ratio, as measured by the DLss during chemotherapy, will identify those patients at risk of developing pain during their treatment.* Ultimately, this will help us identify patients who 1) may benefit from a change in their treatment to prevent CIPN and 2) patients who would be the best candidates for interventional trials testing new drugs for the prevention of PPN.

Aim 1: Demonstrate that the A δ :C pain threshold ratio is significantly higher in patients with painful CIPN than in patients with painless CIPN.

Ovarian cancer annually affects about 20,000 women in the US and causes 14,000 deaths (1999–2012 Cancer Incidence and Mortality Data, <http://www.cdc.gov/cancer/ovarian/statistics/>) (24) Ovarian cancer patients' first line chemotherapy regimen is typically a taxane combined with platinum. These drugs are known to cause CIPN neuropathic symptoms in up to 70% of patients; a large portion of those patients develop painful CIPN (25, 26). The combination of taxane with platinum may increase development of CIPN in 1.5 times compared to just taxane application(25). As a result, ovarian cancer patients have a high overall burden of painful CIPN. Though the exact mechanism of nerve damage may differ between taxanes and platinum drugs, they both result in painful CIPN. Here we will examine the underlying shared pathophysiology

of neuropathic pain. We will evaluate the DLss in [64] ovarian cancer patients with painful and painless neuropathy during initial taxane combined with platinum treatment, to determine their A δ :C pain threshold ratios. Presence or absence of pain will be determined via pain questionnaire and numeric pain scale (27). Enrolling 25 patients with painful CIPN and 25 patients with painless CIPN, we will have 80% power to detect a 1.31 fold A δ :C pain threshold ratio.

Aim 2: Determine the A δ :C ratio over time in patients with CIPN.

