3.3 Enrollment

The target enrollment for this study is 25 patients with painful neuropathy symptoms (Group A) that develop during chemotherapy and 25 patients without painful symptoms during chemotherapy treatment (Group B). Final group assignment takes place on study day 1 when the patient takes a pain questionnaire. There are no differences in study activities between Group A and B. The Stanford Women's Cancer Center sees about 150 new cases of ovarian cancer per year, therefore we believe will able to complete enrollment in 12 months. Patients will be stratified into painful versus painless group based on their first pain assessment inventory. Based on the incidence of painful versus painless neuropathy, we anticipate that Group B will complete enrollment first. Should enrollment in Group A be very slow, our team will consider advertising outside of the Stanford Women's Cancer Center. An additional approach is to increase enrollment in Group B and apply an "unbalanced" design which would increase the number of patients in Group B, but still ensure statistical power of 80%. For example, if only 18 patients with pain are identified, enrolling 39 patients without pain will maintain 80% power. If this step is needed, we will amend the IRB as well as this application. Additionally, we will apply for a no-cost extension to the NIH SBIR that is funding the project.

We understand that patients participating in non-interventional, longitudinal, clinical studies may not follow up for a variety of reasons. To address possible drop out, patients will receive higher compensation for participation in the second test, 75 dollars for the first, 125 dollars for the second. A commonly anticipated drop-out rate is 20% (45), leaving us with approximately 40 patients who we anticipate will complete both time points within the study timeframe. However, it is possible that patients in pain (Group A) may be more likely to follow up with the second test, which would help preserve the power of the study.

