5.0 STATISTICAL CONSIDERATIONS

5.1 Outcome Measurements

5.1.1 Outcome Measure for Aim 1

The primary outcome measure of this study is the difference in the “A δ :C pain threshold ratio” for patients with a painless response to chemotherapy versus painful neuropathy, as measured using the DLss.

The “A δ :C pain threshold ratio” is calculated using the A δ -fiber and C-fiber pain thresholds determined using the protocol outlined in **section 4.4**.

Each patient will have 2 testing sessions:

- 1) 9 weeks +/- 1 week from cycle 1, day 1 of chemotherapy
- 2) 21 weeks +/- 2 weeks after first dose of chemotherapy for ovarian cancer

This is not a safety outcome.

5.1.2 Outcome Measure for Aim 2

The second outcome measure of this study is the correlation between the “A δ :C pain threshold ratio” and the development of pain.

We will generate a Spearman correlation coefficient for the “A δ :C pain threshold ratio” obtained at the first testing session and the presence or absence of pain at the time of the second test.

This is not a safety outcome.

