5.2 Analysis plan

The A δ :C pain threshold ratio will be recorded for each eligible and evaluable patient for both time points. We will calculate the average value of this parameter for each group (A and B) on a logarithmic scale. Then we will use a standard statistical two side t-test to compare the “A δ :C pain threshold ratio” in the painless CIPN group to the painful CIPN group. We hypothesize that the painful CIPN group will have statistically significantly higher value “A δ :C pain threshold ratio” than those without.

To assess whether the “A δ :C pain threshold ratio” predicts future painful or painless CIPN, we will conduct logistic regression analysis of the binary pain value (pain or no pain) at the time of the second testing (independent variable) on the “A δ :C pain threshold ratio” at the time of the first testing (dependent variable). It will allow us to estimate whether the “A δ :C pain threshold ratio” predicts the chances of a patient to develop pain.

As an exploratory analysis, we will explore if the “A δ :C pain threshold ratio” obtained at

the first testing session predicts an increase in the numeric pain scale at the second testing session.

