5.3 Sample size

The power analysis of the preliminary data presented here was conducted by [name] (Stanford). The analysis was done on the natural logarithm scale and converted back using anti-logarithms. The geometric mean (GM) ratio of chemotherapy was 1.58 times the GM for healthy group. The GM in the diabetic group was 1.38 times the GM of the healthy group. The most variable group (Diabetics) had a standard deviation (log scale) of 0.33 and this value was used for sample size calculations.

These calculations showed that sample size of 25 subjects in each group will have 80% power to detect a 1.31 fold A δ :C pain threshold ratio in patients with painful versus painless CIPN. Based on the analysis of our preliminary data, we expect the effect size to be larger than 1.31.

It is possible that we will have more patients accrued to Group B compared to Group A because uncomfortable patients may not want to participate in as great a number. In this case, we will consider use using an “unbalanced” (“non-symmetrical”) statistical design, i.e. a design with unequal number of subjects in the two groups. If we get fewer than 25 patients with pain we will increase the number of patients in the group without pain to preserve the power of 80% in order to detect the effect size. If this approach is necessary, we will apply for a no-cost extension of the NIH SBIR.

Table 5.1 shows several possible combinations of sample sizes which will assure the power 80% to detect the effect size 1.31. The sample sizes were calculated using SAS 9.14 software, procedure proc power. The calculations are based on the use of a t-test on the natural logarithm scale with a standard deviation of 0.33, detectable effect size 0.24 on the log scale.

| Scenario | Subjects with pain | Subjects without pain |
|----------|--------------------|-----------------------|
| 1 | 25 | 25 |
| 2 | 24 | 26 |
| 3 | 23 | 27 |
| 4 | 22 | 28 |
| 5 | 21 | 29 |
| 6 | 20 | 31 |
| 7 | 19 | 34 |
| 8 | 18 | 37 |
| 9 | 17 | 42 |

Based on the new patient volume in the women’s cancer center, we expect to recruit 50 patients in 12 months. However, should the study require a non-symmetric statistical

method and its clear we will not be able to recruit 59 patients (scenario 9), we will we will request a12 month no-cost extension from the NIH/NCI.

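### Group B may include patients with no neuropathy complaints, yet Aim 1, section 5.2 and the power sentence of 5.3 call the pooled test painful versus painless CIPN

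*Combined protocol and SAP*

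**What the plan says.** Section 3.2 Inclusion Criteria, item 3.1.2, requires neuropathic pain of at least 10 out of 100 for Group A. For Group B it accepts either painless neuropathy symptoms or none at all: "strange sensation in fingers and/or toes) or no complaints related to neuropathy". The Appendix A checklist repeats this.

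The comparison of the two groups is then described in two ways.

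- **Narrow (painless CIPN).** Aim 1 in section 1.0 sets out to show that the ratio "is significantly higher in patients with painful CIPN than in patients with painless CIPN", and adds: "Enrolling 25 patients with painful CIPN and 25 patients with painless CIPN, we will have 80% power". Section 5.2 compares the ratio "in the painless CIPN group to the painful CIPN group". The power sentence of 5.3 refers to a 1.31-fold "pain threshold ratio in patients with painful versus painless CIPN".
- **Broad (no pain).** Section 3.3 targets "25 patients without painful symptoms during chemotherapy treatment (Group B"). Section 5.1.1 defines the primary outcome "for patients with a painless response to chemotherapy versus painful neuropathy". The unbalanced option in 5.3 would "increase the number of patients in the group without pain to preserve the power of 80"%, and Table 5.1 labels its columns by presence or absence of pain.

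Section 5.2 averages the log ratio over Groups A and B as enrolled. No section sets a minimum number of painless-CIPN patients in Group B, splits Group B in the analysis, or limits the Aim 1 test to patients with neuropathy.

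**The concern.** The study's argument, set out in sections 1.0 and 2.0, is that loss of nerve fibres does not by itself explain pain. Testing that idea requires painful neuropathy to be compared with painless neuropathy. Under 3.1.2 every Group A patient has neuropathy symptoms, but only some Group B patients do. A difference between the groups could therefore come from pain, from symptomatic neuropathy, or from both.

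Two things are at stake. First, a significant result would be reported in Aim 1's words, as a higher ratio in painful than in painless CIPN, which the pooled test does not establish. Second, the stated 80% power applies to that claim only if all 25 Group B patients have painless CIPN.

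Section 4.4 blurs the grouping further. Its numeric scale asks about overall pain and then defines painful neuropathy as a score of 10 or more. A patient with unrelated pain of 10 to 49 could count as having painful neuropathy under that rule but not under 3.1.2.

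**Working it through.** **Inputs**

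- 25 per group, 80% power, 1.31-fold, log-scale SD 0.33, t-test on the natural-log ratio (5.3); two-sided (5.2). Alpha is not stated; 0.05 is assumed.
- Log-scale effect: 5.3 prints 0.24, but ln 1.31 = 0.270 (and e^0.24 = 1.27). Both are carried through.
- 1.58-fold, chemotherapy group versus healthy (5.3). The preliminary groups were healthy, painful diabetic and painful CIPN (section 2.0, Figure 2), with no painless-CIPN group.
- Share p of Group B without complaints: not given. Aim 1 says symptoms occur in up to 70% of patients, so about 30% or more have none, and under 3.1.2 such patients belong in Group B. Assumed range: 30/40/50%.

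**Step 1: the plan's own figure.** SE = 0.33 × √(1/25 + 1/25) = 0.0933. Noncentrality = 0.270/0.0933 = 2.89, with critical t(48) = 2.011. Power is 80.9%, so 25 per group at 1.31-fold reproduces. At the printed 0.24, power is 71.2%.

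**Step 2: power for painful versus painless CIPN.** The painless-CIPN number is 25(1 − p), and SE = 0.33 × √(1/25 + 1/n).

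| p | Painless CIPN, n | SE | Power at 0.270 | Power at 0.24 | Fold detectable at 80% |
|---|---|---|---|---|---|
| 0 | 25 | 0.0933 | 80.9% | 71.2% | 1.31 |
| 0.3 | 18 | 0.1020 | 73.4% | 63.2% | 1.34 |
| 0.4 | 15 | 0.1078 | 68.5% | 58.3% | 1.36 |
| 0.5 | 12 | 0.1159 | 62.0% | 52.2% | 1.40 |

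In the most unbalanced row of Table 5.1 (17 versus 42), the same shares leave 29/25/21 painless-CIPN patients. Power is then 74.5/71.9/68.5% at 0.270 and 64.4/61.7/58.3% at 0.24.

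**Step 3: what the pooled test does if pain adds nothing.** Let painful and painless CIPN share the same mean, ln f above healthy, and let no-complaint patients sit at c × ln f. The expected difference between A and B is p(1 − c) ln f, a fold of f^(p(1 − c)). With c = 0 this is 1.147/1.201/1.257 for f = 1.58 and 1.084/1.114/1.145 for f = 1.31. Rejection rates by simulation (25 per group, SD 0.33), for p = 30/40/50%:

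| No-complaint patients' ratios | f = 1.58 | f = 1.31 |
|---|---|---|
| Same as painless CIPN (c = 1) | 5/5/5% | 5/5/5% |
| Half the log effect (c = 0.5) | 11/15/21% | 7/9/11% |
| Healthy (c = 0, worst case) | 26/41/58% | 13/19/28% |

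The rate is also 5% if symptomatic neuropathy has not yet raised the ratio at week 9, which Aim 2 leaves open.

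**Step 4: the section 4.4 rule.** If it also placed symptom-free patients in Group A, say 20% (an assumption for illustration), the worst case falls to 7/13/23% (f = 1.58) or 6/8/13% (f = 1.31).

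**Step 5: the alternative contrast.** In a three-group model with f = 1.58, c = 0 and 18/15/12 painless-CIPN patients, the painful-versus-painless contrast rejects in 5.0/5.1/5.0% of trials. It holds its level where the pooled test does not.

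**The case against.** The strongest reply is that the operative text already describes painful versus not painful. Section 5.2 averages over Groups A and B, and its hypothesis sentence ends by comparing the painful group with those without. Sections 3.3 and 5.1.1 and Table 5.1 also fit Group B as enrolled. On that reading, only loose wording remains. This stands as far as enrolment goes: admitting no-complaint patients is defensible, and it is useful for Aim 2, which needs patients who may yet develop pain. It does not rescue the aim, the sentence that names the test, or the two power sentences, because those determine what will be claimed.

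A second reply is that Aim 1 also mentions 64 patients, in brackets. If that meant 25 versus 39 (an assumption), shares of 30/40/50% would leave 27/23/19 painless-CIPN patients and 82/79/75% power at 0.270. The power loss would then be small. But the figure is unexplained and disagrees with 25 plus 25, and a larger Group B does not remove the mixing.

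Third, the error rates rest on assumptions, and the 58% needs several unfavourable ones at once. With a 20% share and half the effect, the rate is only 8% (1.58-fold) or 6% (1.31-fold). That is correct, so bias is a possibility here and not a finding.

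Finally, eligibility source files may allow Group B to be split afterwards. The first questionnaire items were also not available to me, so a suitable field may already exist. Either would make the fix easier, but neither makes the split a prespecified analysis. That the checklist title calls this a feasibility study lowers the stakes but does not make the label right.

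**Conclusion.** The concern holds and should be fixed; the fault lies in the claim and its power statement, not in whom the study enrols. The mismatch between criterion 3.1.2 and the narrow label is certain and needs no assumption. So is the fact that, with 25 in Group B, each no-complaint patient takes the painless-CIPN count below the 25 on which Aim 1 bases its power.

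The size of the consequences is uncertain. The power loss depends on the assumed 30 to 50% share, on SD 0.33 and on two-sided 0.05. Any bias depends also on the no-complaint patients' ratios, which the documents do not give, and it may be nil.

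The preliminary 1.58-fold difference does not support the expectation in 5.3 of an effect above 1.31 for painful versus painless CIPN, because its comparator was healthy volunteers.

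**What to change.** Keep enrolment, sample size and the pooled test, and make these changes:

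1. Record for every patient at visit 1 whether neuropathy symptoms are painful, painless or absent, so that it is known which alternative of 3.1.2 each Group B patient met. If a form already captures this, name it as the analysis variable. Reconcile the pain-scale definition in 4.4 with 3.1.2.
2. In Aim 1, 5.2 and 5.3, describe A versus all of B as painful CIPN versus no painful neuropathy.
3. Prespecify the painful-versus-painless-CIPN contrast on the log ratio in a three-group model, report it with a 95% CI, and rest any claim about painful versus painless CIPN on it alone.
4. State that the 80% power belongs to A versus all of B, correct the Aim 1 sentence about 25 painless-CIPN patients, and give the contrast's power for the number of such patients expected.
5. Qualify the expectation of an effect above 1.31, since its basis is a healthy comparator.

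The cost is one CRF field, one further analysis and wording changes. The drawback is a lower stated power for the narrower claim, as shown in the working, so a non-significant contrast would be inconclusive. If the sponsor wants 25 painless-CIPN patients on average, Group B would need 25/(1 − p), that is 36/42/50 patients at shares of 30/40/50%. Section 5.3 already foresees enlarging Group B, though for a different reason, but this is optional.

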3.2 Exclusion Criteria

- 3.2.1 Has received systemic chemotherapy for ovarian cancer or cancer of mullerian origin other than first-line treatment with a taxane + platinum based chemotherapy regimen.
- 3.2.2 Has received investigational drugs suspected to cause peripheral neuropathy. No concurrent investigational drugs may be used.
- 3.2.3 Has a history of:
 - neuropathy or numbness/tingling suspicious for neuropathy prior to the first dose of chemotherapy for ovarian cancer
 - history of prior treatment for other cancers that includes drugs known to cause neuropathy. These drugs include but are not limited to vinca-alkaloids, platinums, taxanes, bortezomib.
 - B12 deficiency
 - known peripheral vascular disease
 - chronic daily headache or headache more than 14 days of the month

3.2.4 Has pain rated 50 or higher on a scale of 0-100, with 0 = no pain at all and 100 = worst pain imaginable on the day of the first DLss test.

3.2.5 Known pregnant or nursing patients.

3.2.6 Cancer survivors who have previous exposure to medications or chemotherapy that cause neuropathy are excluded from this study.

3.2.7 Patients who are known to be HIV-positive will be excluded as HAART and HIV itself are known to cause peripheral neuropathy.

3.2.8 Patients who do not speak or read English are excluded from this study.

3.3 Enrollment

The target enrollment for this study is 25 patients with painful neuropathy symptoms (Group A) that develop during chemotherapy and 25 patients without painful symptoms during chemotherapy treatment (Group B). Final group assignment takes place on study day 1 when the patient takes a pain questionnaire. There are no differences in study activities between Group A and B. The Stanford Women's Cancer Center sees about 150 new cases of ovarian cancer per year, therefore we believe will able to complete enrollment in 12 months. Patients will be stratified into painful versus painless group based on their first pain assessment inventory. Based on the incidence of painful versus painless neuropathy, we anticipate that Group B will complete enrollment first. Should enrollment in Group A be very slow, our team will consider advertising outside of the Stanford Women's Cancer Center. An additional approach is to increase enrollment in Group B and apply an "unbalanced" design which would increase the number of patients in Group B, but still ensure statistical power of 80%. For example, if only 18 patients with pain are identified, enrolling 39 patients without pain will maintain 80% power. If this step is needed, we will amend the IRB as well as this application. Additionally, we will apply for a no-cost extension to the NIH SBIR that is funding the project.

We understand that patients participating in non-interventional, longitudinal, clinical studies may not follow up for a variety of reasons. To address possible drop out, patients will receive higher compensation for participation in the second test, 75 dollars for the first, 125 dollars for the second. A commonly anticipated drop-out rate is 20% (45), leaving us with approximately 40 patients who we anticipate will complete both time points within the study timeframe. However, it is possible that patients in pain (Group A) may be more likely to follow up with the second test, which would help preserve the power of the study.

